### Biomarkers

The pharmacodynamic parameters listed in Section [2.1](#) and [2.2](#) for cGMP will be calculated according to the relevant BI internal procedures.

### 7.3.2 Primary endpoint analyses

#### Maximum exposure-related change from baseline of cGMP in CSF

The maximum exposure-related change from baseline in cGMP in CSF will be explored using an ANCOVA model, which can be described by the following equation:

$$y_{i,j} = \alpha \ln(\text{cGMP}_{\text{base},i}) + \text{treatment}_j + e_{i,j},$$

Where

$y_{i,j}$  = natural logarithm of the ratio  $\text{cGMP}_{\text{max},i}/\text{cGMP}_{\text{base},i}$  for subject  $i$  receiving treatment  $j$

$\alpha$  = slope parameter for the baseline effect

$\text{cGMP}_{\text{base},i}$  =  $\text{cGMP}_{\text{base}}$  for subject  $i$

$\text{treatment}_j$  = the  $j^{\text{th}}$  treatment effect, (placebo, 2.5mg, 10mg, 20 mg, 40mg)

$e_{i,j}$  = random error associated with  $i^{\text{th}}$  subject who received treatment  $j$

For the endpoint  $\text{cGMP}_{\text{max}}/\text{cGMP}_{\text{base}}$ , the difference between the expected means for  $\ln(T) - \ln(R)$  will be estimated by the difference in the corresponding least square means (point estimate) and two-sided 90% confidence intervals based on the t-distribution will be computed. These quantities will then be back-transformed to the original scale to give the point estimator and interval estimates.

Estimates will be computed for the different dose groups (T) versus placebo (R), respectively.

Final analysis will include data from all dose groups.

#### Cmax ratio of BI 474121 in CSF compared to plasma

The relationship between exposures of BI 474121 in CSF compared to plasma will be explored using an ANOVA model, which can be described by the following equation:

$$\ln(C_{\max_{i,j,k}}) = \text{pkmatrix}_k + \text{treatment}_j + e_{i,j,k}$$

where

$\text{pkmatrix}_k$  =  $k^{\text{th}}$  substance effect, (CSF or plasma)

$\text{treatment}_j$  = the  $j^{\text{th}}$  treatment effect, (2.5mg, 10mg, 20 mg, 40mg)

$e_{i,j,k}$  = random error associated with  $i^{\text{th}}$  subject who received treatment  $j$  in substance  $k$

[figure not shown]
All effects will be considered as fixed. Estimates will be provided by treatment as well as overall.

The pharmacokinetic parameter  $C_{\max}$  will be log transformed (natural logarithm) prior to fitting the ANOVA model. The difference between the expected means for  $\ln(C_{\max}$  in CSF)- $\ln(C_{\max}$  in plasma) will be estimated by the difference in the corresponding least square means (point estimate) and two-sided 90% confidence intervals based on the t-distribution will be computed. These quantities will then be back-transformed to the original scale to give the point estimator and interval estimates for the geometric mean of the ratio between exposure in CSF and exposure in plasma. Estimates will be computed separately for each treatment.

Additionally, the primary endpoints will be analysed using descriptive statistics.

### **7.3.3 Secondary endpoint analyses**

The secondary endpoints (refer to Section [2.1.3](#)) will be analysed using descriptive statistics.

### 7.3.5 Safety analyses

Safety will be analysed based on the assessments described in Section [2.2.2.2](#). All treated subjects (TS, refer to Section [7.3](#)) will be included in the safety analysis. Safety analyses will be descriptive in nature and based on BI standards. No hypothesis testing is planned.

For all analyses, the treatment actually administered (= treatment at onset) to the subject will be used (any deviations from the randomised treatment will be discussed in the minutes of the Report Planning Meeting).

Treatments will be compared in a descriptive way. Tabulations of frequencies/proportions will be used to evaluate categorical (qualitative) data, and tabulations of descriptive statistics will be used to analyse continuous (quantitative) data.

Measurements (such as vital signs, or laboratory parameters) or AEs will be assigned to treatments (see Section [4.1](#)) based on the actual treatment at the planned time of the measurement or on the recorded time of AE onset (concept of treatment emergent AEs). Therefore, measurements planned or AEs recorded prior to first intake of trial medication will be assigned to the screening period, those between first trial medication intake and end of REP (see Section [1.2.2](#)) will be assigned to the treatment period. Events occurring after the REP but prior to end of trial termination date will be assigned to 'follow-up'. These assignments including the corresponding time intervals will be defined in detail in the TSAP. Note that AEs

occurring after the last per protocol contact but entered before final database lock will be reported to Pharmacovigilance only and will not be captured in the trial database.

Additionally, further treatment intervals (analysing treatments) may be defined in the TSAP in order to provide summary statistics for time intervals, on-treatment totals, or periods without treatment effects (such as screening and follow-up intervals).

Adverse events will be coded using the Medical Dictionary for Regulatory Activities (MedDRA). Frequency, severity, and causal relationship of AEs will be tabulated by treatment, system organ class, and preferred term. SAEs, AESIs (see Section [5.2.5.1](#)), and other significant AEs (according to ICH E3) will be listed separately.

Previous and concomitant therapies will be presented per treatment group without consideration of time intervals and treatment periods.

Laboratory data will be compared to their reference ranges. Values outside the reference range as well as values defined as possibly clinically significant will be highlighted in the listings. Additionally, differences from baseline will be evaluated.

Vital signs or other safety-relevant data will be assessed with regard to possible on-treatment changes from baseline.

Relevant ECG findings will be reported as AEs.

#### **7.4 INTERIM ANALYSIS**

No formal interim analyses is planned.

However, a preliminary analysis of PK and PD parameters in CSF and plasma (including  $C_{\max}$  and  $AUC_{0-24}$  for BI 474121 in plasma) provided as individual values and gMeans per dose level, will be performed after Part 1 and Part 2 (if applicable). These preliminary analyses will additionally comprise analyses of safety parameters.

In contrast to the final PK and PD calculations, the preliminary analysis will be based on planned sampling times rather than on actual times. Therefore, minor deviations of preliminary and final results may occur. The preliminary results will be distributed to the investigator and the trial team.

Depending on the results of available preliminary PK analyses, the tolerability and safety of the compound, additional PK preliminary analysis may be performed based on the request of the Clinical Trial Leader, the investigator, or Trial Clinical Pharmacokineticist. No formal preliminary PK and PD report will be written.

In addition, after Part 1 and Part 2 (if applicable) the ANCOVA model for evaluation of maximum exposure-related changes in cGMP as described in Section [7.3.1](#) will be computed. After trial Part 1 the data (treatment B and placebo) will be analysed, after trial Part 2 the data from treatment A and placebo (from part 1) will be analysed.

If the placebo adjusted change in  $cGMP_{\max}$  is not considered sufficient, the sponsor reserves the right to terminate the trial.

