### PD criterion (see criterion 1, Section [3.3.4.3](#)):

If the desired PD effect is observed after administration of 20 mg BI 474121, the trial continues with Part 3 (given the observed safety profile allows to proceed), i.e. Part 2 will be omitted.

If the desired PD effect is not observed after administration of 20 mg BI 474121, the trial may continue with Part 2 (DG 2, 40 mg), if the following PK and safety criteria are fulfilled.

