### Safety criterion:

- DG 1 (20 mg) was safe and showed acceptable tolerability

### Minimum data set to be reviewed after Part 1 (DG 1, 20 mg) for escalating to Part 2

PD data from at least 4 subjects on active and at least 3 subjects on placebo need to be evaluated to assess the PD effect after trial Part 1.

If the desired PD effect is not observed in Part 1, the following minimum data from 4 subjects on active need to be evaluated to assess whether it is safe to proceed to Part 2 (40 mg) based on the assessment of

- PK in plasma up to at least 24 hours post dosing
- Adverse events, vital signs, ECG, safety lab up to at least 24 hours post dosing

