#### **Minimum data set to be reviewed after Part 2 (DG 2, 40 mg BI 474121)**

Data from at least 4 subjects on active (from DG 2) and at least 3 subjects on placebo (from DG 1) needs to be evaluated to assess the PD effect.

For safety data, no minimum data set is specified, since in Part 3 of the trial lower doses are administered. However, the documented data review includes the review of all available safety data.

The decision about the further conduct of the trial based on the preliminary data analysis will be made jointly by the Principal Investigator (PI), the Team Member Medicine (TMM), and the Clinical Trial Leader (CTL) or their respective authorised deputy. The documented data reviews may be conducted by video/telephone conference. The CTL is responsible for the organisation and minutes of the reviews. Minutes will be signed off by the PI (or an authorised deputy), the CTL (or authorised deputy), and the TMM and will be filed in the ISF and TMF.

**Conduct of Part 3 (DG 3, 10 mg BI 474121 and DG 4, 2.5 mg BI 474121) – if applicable:** 8 subjects will receive randomized treatment, all subjects on active, 4 subjects in DG 3 (10 mg) and 4 subjects in DG 4 (2.5 mg).

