#### Section 7.3.1 of the CTP:

*Maximum measured exposure-related cGMP concentration in CSF (cGMPmax):*

*In subjects treated with BI 474121 this is the maximum cGMP value measured within 1 h prior and 4 h post BI 474121 Cmax in CSF.*

*For subjects treated with placebo, this is the maximum cGMP value measured within 1 h prior to and 4 h after the median BI 474121 tmax in CSF of the BI 474121 treated subjects.*

*That means, when comparing placebo and 20 mg (after Part 1), the median BI 474121 tmax in CSF of the subjects treated with 20 mg is used, and when comparing placebo and 40 mg (after Part 2), the median BI 474121 tmax in CSF of the subjects treated with 40 mg will be considered. For the final analysis, the median BI 474121 tmax in CSF for subjects treated with the highest investigated dose group will be used.*

*The tmax values of BI 474121 in CSF used to determine the time window for cGMP are based on planned times. In case one of the considered median BI 474121 tmax in CSF is not defined unequivocally the smallest planned time fulfilling the median properties will be used.*

Additionally the minimum measured exposure-related cGMP concentration in CSF (cGMPmin) will be determined, using the same time interval around Cmax of BI 474121 in CSF as used for cGMPmax.

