### Interim analyses

No inferential statistical interim analysis is planned. Preliminary analyses of safety, PK and PD parameters were performed after trial part 1 and 2 (including  $C_{max}$  and  $AUC_{0-24}$  of BI 474121 in plasma and cGMP in CSF). The preliminary analyses after Part 1 and 2 were done to evaluate the proof-of-pharmacological-principal for BI 474121. Furthermore a preliminary analysis after Part 3 (PK and PD only) will be done to support dose finding for trial 1411-0003. In contrast to the final PK and PD calculations, the preliminary analysis will be based on planned sampling times rather than on actual times. All details about the preliminary analyses are described in a trial-specific logistics plan (9).

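### Should the cGMP ANCOVA after Part 2 have included the 20 mg subjects as well as 40 mg and placebo?

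*Protocol*

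**What the plan says.** Protocol section 7.4 plans no formal interim analysis, but it does plan preliminary analyses after Part 1 and, if it is run, after Part 2. Each includes the cGMP ANCOVA. After Part 1 the model is fitted to 20 mg (treatment B) and placebo. For the next look, "after trial Part 2 the data from treatment A and placebo (from part 1) will be analysed". If the placebo-adjusted change in maximum cGMP "is not considered sufficient, the sponsor reserves the right to terminate the trial".

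Section 3.1 sets minimum data for each look. After Part 1, "PD data from at least 4 subjects on active and at least 3 subjects on placebo need to be evaluated". After Part 2 the minimum is again four on active (now 40 mg) and three on placebo, the latter carried over from Part 1.

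The model in Protocol section 7.3.2 and SAP section 7.4.1.1 regresses the log ratio to baseline on log baseline and treatment, with one slope and one residual variance, and gives two-sided 90% intervals. Section 7.3.2 adds: "Final analysis will include data from all dose groups".

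SAP section 5.1 ties the placebo time window to the comparison being made: "when comparing placebo and 40 mg (after Part 2), the median BI 474121" CSF tmax of the 40 mg subjects is the reference. After Part 1 the 20 mg median plays that role. The interim paragraph of SAP section 7 reports: "Preliminary analyses of safety, PK and PD parameters were performed after trial part 1 and 2".

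**The concern.** Part 2 starts only after Part 1 has been reviewed, so the 20 mg data are in hand when the 40 mg result is assessed. In an ANCOVA with a common slope and variance, a third group helps to estimate both, even when the contrast of interest does not involve it. The final analysis makes exactly that assumption across all dose groups, and the visible text gives no reason for dropping it at the second look.

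The look may rest on as few as seven subjects, which leaves four error degrees of freedom, and it bears on whether the sponsor ends the trial before Part 3. An imprecise estimate there could stop a useful trial or let a futile one continue. The 20 mg data also came from volunteers who underwent spinal catheterisation, which is a reason to use them fully.

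**Working it through.** The documents state no power, standard deviation or interval width for this contrast, so there is no planned figure to reproduce. The check compares the two-group fit with a fit that adds 20 mg as a third treatment level.

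**Inputs.** Planned sizes (Protocol section 3.1): 4 placebo, 6 on 20 mg, 6 on 40 mg. Minimum after Part 2: 3 placebo, 4 on 40 mg; for 20 mg at that minimum, both 4 and 6 are tried. Interval: two-sided 90%. The residual SD of the log ratio is not given, so results are in units of that SD and the relative comparisons do not depend on it.

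**Degrees of freedom**, N − groups − 1, with t at 0.95:
- Planned: 10 − 2 − 1 = 7 (t = 1.895); with 20 mg, 16 − 3 − 1 = 12 (t = 1.782).
- Minimum: 7 − 2 − 1 = 4 (t = 2.132); with four on 20 mg, 11 − 3 − 1 = 7 (t = 1.895); with six, 13 − 3 − 1 = 9 (t = 1.833).

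**SD of the adjusted 40 mg minus placebo estimate**, for a normally distributed covariate: √[(1/n₄₀ + 1/n_P)(1 + 1/(v − 2))], with v = N − groups.
- Planned, two groups (v = 8): √(0.4167 × 7/6) = 0.697.
- Planned, with 20 mg (v = 13): √(0.4167 × 12/11) = 0.674, which is 3% lower.
- Minimum, two groups (v = 5): √(0.5833 × 4/3) = 0.882.
- Minimum, four added (v = 8): √(0.5833 × 7/6) = 0.825, 6% lower.
- Minimum, six added (v = 10): √(0.5833 × 9/8) = 0.810, 8% lower.

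The gain is small because the number of subjects on 40 mg and placebo does not change. Only the baseline slope is better estimated.

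**Mean 90% half-width**, from simulated ANCOVA fits with equal variances:

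| Data set | Two groups | With 20 mg | Change |
|---|---|---|---|
| Planned, six added | 1.27 | 1.17 | −7% |
| Minimum, four added | 1.73 | 1.50 | −13% |
| Minimum, six added | 1.73 | 1.44 | −17% |

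Coverage was about 90% in every case, so the two-group fit is valid under its model. Even with all assumptions met, the pooled interval was the narrower one in only about 68% of single data sets at planned size (72% at the minimum).

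**On the fold scale**, for an assumed residual log SD of 0.15 to 0.35, the multiplicative margin exp(half-width × SD) at planned size moves from 1.21–1.56 to 1.19–1.51. At the minimum it moves from 1.30–1.83 to 1.25–1.69 (four added) or 1.24–1.65 (six added).

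**If the 20 mg residual SD differs from the other two groups** (planned size, pooled fit):

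| 20 mg SD relative to the others | Coverage of 90% interval | Mean half-width |
|---|---|---|
| 0.5 | 84.0% | 0.99 |
| 0.75 | 87.1% | 1.07 |
| 1 | 90.0% | 1.17 |
| 1.25 | 92.5% | 1.29 |
| 1.5 | 94.3% | 1.43 |
| 2 | 96.8% | 1.71 |

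The two-group fit does not use the 20 mg subjects and stays at 1.27 with 90% coverage throughout. At a ratio of 1.25 the average gain from pooling has already become a small loss (1.29 against 1.27). Below 1, the narrower interval is partly bought with lost coverage.

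**The case for a change.** The strongest argument for pooling is consistency. The sponsor accepts a common slope and variance in the final model, so applying them one step earlier adds no new kind of assumption. No new endpoint definition would be needed either: each active subject's cGMP window follows his own CSF maximum, and the placebo window could stay on the 40 mg median. At the minimum data set the gain in interval width, 13% to 17%, is not trivial. The change would cost one sentence, and the pairwise fit could be kept as a check.

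Most of this is true. The arithmetic stands, and pooling would have been a reasonable choice too. What does not follow is that the pairwise fit is deficient:

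- Accepting equal variance in a final exploratory model does not oblige the sponsor to let a go/no-go contrast depend on a third group's variance. No residual SD is given for any group, so equality cannot be checked from the documents.
- The larger figures apply only if 40 mg and placebo both shrink to their minimum. Protocol section 7.7 says the numbers in Parts 1 and 2 were raised because of the risk of missing data.
- The visible rule turns on the size of the placebo-adjusted change, and for that quantity the planned-size gain is about 3%. The PD criterion to which section 3.1 refers is not visible, so a role for the interval can be neither shown nor excluded.
- The 20 mg data are not ignored. They are modelled against placebo after Part 1, and section 7.4 provides individual values and geometric means for each dose level.

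**Conclusion.** The concern does not hold. The post-Part 2 ANCOVA on 40 mg and placebo is valid, matches the comparison-specific placebo window in SAP section 5.1, and contradicts nothing in either document. Leaving out 20 mg costs about 3% in the SD of the estimate and about 7% in mean interval width at planned size, and 6% to 8% and 13% to 17% at the minimum. These figures assume normal errors, a normally distributed log baseline, a common slope and equal residual variances. The benefit shrinks, reverses or costs coverage when the 20 mg variance differs, so the choice trades a little precision for robustness and either side can be defended.

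The setting supports this reading. Protocol section 7.2 plans no hypothesis tests and treats intervals as estimates, and section 7.7 states that the sample size has no power basis. The final ANCOVA supplies the 40 mg versus placebo contrast from all dose groups. The SAP records that the looks after Parts 1 and 2 had already taken place, so new wording could no longer inform that decision.

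Two limits remain. The 40 mg versus placebo comparison is non-randomised and uses placebo subjects from Part 1, which Protocol section 3.2 discloses and accepts; adding 20 mg would not alter that. The logistics plan that holds the details of the preliminary analyses was not available, so whether a pooled fit was also run is unknown.

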## **7.5 HANDLING OF MISSING DATA**

### **7.5.1 Safety**

It is not planned to impute missing values for safety parameters.

### **7.5.2 Pharmacokinetics**

Handling of missing PK data will be performed according to the relevant BI internal procedures.

PK parameters that cannot be reasonably calculated based on the available drug concentration-time data will not be imputed.

### **7.5.3 Pharmacodynamics**

It is not planned to impute missing values for safety parameters.

## **7.6 RANDOMISATION**

In Part 1 subjects will be randomised to the two treatments in a 3:2 ratio, which reflects the ratio of subjects receiving active drug to placebo. In Part 2 all subjects will receive active treatment. In Part 3 subjects will be randomised to the two treatment groups in a 1:1 ratio.

The sponsor will arrange for the randomisation as well as packaging and labelling of study medication. The randomisation lists will be generated using a validated system, which involves a pseudo-random number generator and a supplied seed number so that the resulting allocation of medication numbers to treatment is both reproducible and non-predictable.

The randomisation lists will contain mirror sets for part 1 and part 3 to allow for subject replacement (refer to Section [3.3.5](#)).

## **7.7 DETERMINATION OF SAMPLE SIZE**

It is planned to include a total of 24 subjects in this trial. The planned sample size is not based on a power calculation. The size of 4 subjects for dose group 3 and 4 (all on active treatment) is commonly used in studies of the present type and is in general considered as sufficient for the exploratory evaluation of single dose safety, pharmacokinetics, and pharmacodynamics.

The data of study Part 1 and 2 is used to decide on the further conduct of the trial. Therefore, in this part the sample size has been increased to 12 active subjects and 4 control subjects, to reduce the risk for missing data (see Section [3.1](#)).

## **8. INFORMED CONSENT, TRIAL RECORDS, DATA PROTECTION, PUBLICATION POLICY, AND ADMINISTRATIVE STRUCTURE**

The trial will be carried out in compliance with the protocol, the ethical principles laid down in the Declaration of Helsinki, in accordance with the ICH Harmonized Guideline for Good Clinical Practice (GCP), relevant BI Standard Operating Procedures (SOPs), the EU regulation 536/2014, and other relevant regulations. Investigators and site staff must adhere to these principles.

Standard medical care (prophylactic, diagnostic, and therapeutic procedures) remains the responsibility of the subject's treating physician.

The investigator will inform the sponsor immediately of any urgent safety measures taken to protect the trial subjects against any immediate hazard, as well as of any serious breaches of the protocol or of ICH GCP.

The Boehringer Ingelheim transparency and publication policy can be found on the following web page: [trials.boehringer-ingelheim.com](http://trials.boehringer-ingelheim.com). The rights of the investigator and of the sponsor with regard to publication of the results of this trial are described in the investigator contract. As a general rule, no trial results should be published prior to archiving of the CTR.

The terms and conditions of the insurance coverage are made available to the investigator and the subjects, and are stored in the ISF.

### **8.1 TRIAL APPROVAL, SUBJECT INFORMATION, INFORMED CONSENT**

This trial will be initiated only after all required legal documentation has been reviewed and approved by the respective Institutional Review Board (IRB) / Independent Ethics Committee (IEC) and competent authority (CA) according to national and international regulations. The same applies for the implementation of changes introduced by amendments.

Prior to a subject's participation in the trial, written informed consent must be obtained from each subject (or the subject's legally accepted representative) according to ICH-GCP and to the regulatory and legal requirements of the participating country. Each signature must be personally dated by each signatory and the informed consent and any additional subject-information form retained by the investigator as part of the trial records. A signed copy of the informed consent and any additional subject information must be given to each subject or the subject's legally accepted representative.

The subject must be given sufficient time to consider participation in the trial. The investigator or delegate obtains written consent of the subject's own free will with the informed consent form after confirming that the subject understands the contents. The investigator or [REDACTED] delegate must sign (or place a seal on) and date the informed consent form. If a trial collaborator has given a supplementary explanation, the trial collaborator also signs (or places a seal on) and dates the informed consent. For subjects enrolled during the COVID-19 pandemic: In addition to the study specific informed consent, separate written consent will be obtained for testing on SARS-CoV-2 infection.

Re-consenting may become necessary when new relevant information becomes available and should be conducted according to the sponsor's instructions.

The consent and re-consenting process should be properly documented in the source documentation.

